## **Appendix K    Guidance on contraceptive methods and collection of pregnancy information**

### **DEFINITIONS**

#### **Nonreproductive potential**

1. Premenopausal female with 1 of the following:
  - Documented hysterectomy,
  - Documented bilateral salpingectomy,
  - Documented bilateral oophorectomy.
2. Postmenopausal
  - A postmenopausal state is defined as no menses for 12 months without an alternative medical cause. A high follicle stimulating hormone (FSH) level in the postmenopausal range may be used to confirm a postmenopausal state in women not using hormonal contraception or hormonal replacement therapy (HRT). However, in the absence of 12 months of amenorrhea, a single FSH measurement is insufficient.
  - Females on hormone replacement therapy (HRT) and whose menopausal status is in doubt will be required to use 1 of the highly effective contraception methods if they wish to continue their HRT during the study. Otherwise, they must discontinue HRT to allow confirmation of postmenopausal status before study enrolment.

#### **Reproductive potential (WOCBP)**

A woman is considered of reproductive potential (WOCBP), ie, fertile, following menarche and until becoming postmenopausal unless permanently sterile. Permanent sterilization methods include hysterectomy, bilateral salpingectomy and bilateral oophorectomy.

### **CONTRACEPTIVE GUIDANCE**

#### **Male subjects**

- Male subjects with heterosexual partners of reproductive potential (WOCBP) are eligible to participate if they agree to use the following during the protocol defined timeline:
  - Refrain from donating sperm,  
**and**
  - At least 1 of the following conditions applies:
    - Are and agree to remain abstinent from penile-vaginal intercourse on a long term and persistent basis, when this is their preferred and usual lifestyle,  
**or**
    - Agree to use a male condom plus an additional contraceptive method with a failure rate of <1% per year (see table for female subjects).
- Men with a pregnant or breastfeeding partner must agree to remain abstinent from penile-vaginal intercourse or use a male condom for the time defined in the protocol.

### **Highly Effective Contraceptive Methods That Are User Dependent**

*Failure rate of <1% per year when used consistently and correctlya*

- Combined (estrogen- and progestogen-containing ) hormonal contraception associated with inhibition of ovulation b
  - oral
  - intravaginal
  - transdermal
- Progestogen-only hormone contraception associated with inhibition of ovulation b
  - oral
  - injectable

### **Highly Effective Methods That Are User Independent**

- Implantable progestogen-only hormone contraception associated with inhibition of ovulation b
- Intrauterine device (IUD)
- Intrauterine hormone-releasing system (IUS)
- Bilateral tubal occlusion
- Vasectomized partner  
(*Vasectomized partner is a highly effective contraceptive method provided that the partner is the sole sexual partner of the woman of childbearing potential and the absence of sperm has been confirmed. If not, an additional highly effective method(s) of contraception should be used. Spermatogenesis cycle is approximately 90 days.*)
- Sexual abstinence  
(*Sexual abstinence is considered a highly effective method only if defined as refraining from heterosexual intercourse during the entire period of risk associated with the study drug. The reliability of sexual abstinence needs to be evaluated in relation to the duration of the study and the preferred and usual lifestyle of the subject.*)

### **NOTES:**

- a) Typical use failure rates may differ from those when used consistently and correctly. Use should be consistent with local regulations regarding the use of contraceptive methods for subjects participating in clinical studies.
- b) Hormonal contraception may be susceptible to interaction with the study drug, which may reduce the efficacy of the contraceptive method. In this case TWO highly effective methods of contraception should be used during the treatment period and for at least [XX, corresponding to time needed to eliminate study treatment plus 30 days for study treatments with genotoxic potential] after the last dose of study treatment.

### Female subjects:

Highly Effective Contraceptive Methods That Are User Dependent	
Failure rate of <1% per year when used consistently and correctlya	
• Combined (estrogen- and progestogen-containing ) hormonal contraception associated with inhibition of ovulation b	- oral - intravaginal - transdermal
• Progestogen-only hormone contraception associated with inhibition of ovulation b	- oral - injectable
Highly Effective Methods That Are User Independent	
• Implantable progestogen-only hormone contraception associated with inhibition of ovulation b	
• Intrauterine device (IUD)	
• Intrauterine hormone-releasing system (IUS)	
• Bilateral tubal occlusion	
• Vasectomized partner	(Vasectomized partner is a highly effective contraceptive method provided that the partner is the sole sexual partner of the woman of childbearing potential and the absence of sperm has been confirmed. If not, an additional highly effective method(s) of contraception should be used. Spermatogenesis cycle is approximately 90 days.)
• Sexual abstinence	(Sexual abstinence is considered a highly effective method only if defined as refraining from heterosexual intercourse during the entire period of risk associated with the study drug. The reliability of sexual abstinence needs to be evaluated in relation to the duration of the study and the preferred and usual lifestyle of the subject.)
NOTES:	
a)	Typical use failure rates may differ from those when used consistently and correctly. Use should be consistent with local regulations regarding the use of contraceptive methods for subjects participating in clinical studies.
b)	Hormonal contraception may be susceptible to interaction with the study drug, which may reduce the efficacy of the contraceptive method. In this case TWO highly effective methods of contraception should be used during the treatment period and for at least [XX, corresponding to time needed to eliminate study treatment plus 30 days for study treatments with genotoxic potential] after the last dose of study treatment.

## COLLECTION OF PREGNANCY INFORMATION

### Male subjects with partners of reproductive potential who become pregnant

- The Investigator will attempt to collect pregnancy information on any female partner of a male study subject who becomes pregnant while participating in this study. This applies only to subjects who receive study treatment.
- After obtaining the necessary signed informed consent from the pregnant female partner directly, the Investigator will record pregnancy information on the appropriate form and submit it to the Sponsor within 24 hours of learning of the partner's pregnancy
- Partner will also be followed to determine the outcome of the pregnancy. Information on the status of the mother and child will be forwarded to the Sponsor.
- Generally, follow-up will be no longer than 6 to 8 weeks following the estimated delivery date. Any termination of the pregnancy will be reported regardless of fetal status (presence or absence of anomalies) or indication for procedure

### **Female subjects who become pregnant**

- The Investigator will collect pregnancy information on any female subject, who becomes pregnant while participating in this study
- Information will be recorded on the appropriate form and submitted to the Sponsor within 24 hours of learning of a participant's pregnancy.
- Participant will be followed to determine the outcome of the pregnancy. The Investigator will collect follow-up information on participant and neonate, which will be forwarded to the Sponsor. Generally, follow-up will not be required for longer than 6 to 8 weeks beyond the estimated delivery date.
- Any termination of pregnancy will be reported, regardless of fetal status (presence or absence of anomalies) or indication for procedure.
- While pregnancy itself is not considered to be an AE or SAE, any pregnancy complication or elective termination of a pregnancy will be reported as an AE or SAE.
- A spontaneous abortion is always considered to be an SAE and will be reported as such.
- Any SAE occurring as a result of a post-study pregnancy which is considered reasonably related to the study treatment by the Investigator, will be reported to the Sponsor as described in [Section 10.4](#). While the Investigator is not obligated to actively seek this information in former study subjects, he or she may learn of an SAE through spontaneous reporting.

## **Appendix L    Country-specific requirement**

Will be added as necessary by the concerned country.

## LIST OF ABBREVIATIONS AND DEFINITION OF TERMS

AE:	adverse event
AESI:	adverse event of special interest
ALP:	alkaline phosphatase
ALT:	alanine aminotransferase
AST:	aspartate aminotransferase
ATC:	anatomical therapeutic chemical
CHD:	coronary heart disease
CI:	confidence interval
CV:	cardiovascular
CVD:	cardiovascular disease
DBP:	diastolic blood pressure
ECG:	electrocardiogram
eCRF:	electronic case report form
eGFR:	estimated glomerular filtration rate
EOS:	end-of-study
EOT:	end-of-treatment
FDA:	Food and Drug Administration
FH:	familial hypercholesterolemia
HbA1c:	glycated hemoglobin A1c
HDL-C:	high density lipoprotein cholesterol
heFH:	heterozygous familial hypercholesterolemia
HLGT:	high level group term
HLT:	high level term
HR:	heart rate
IMP:	investigational medicinal product
IVRS:	interactive voice response system
IWRS:	interactive web response system
LDL-C:	low density lipoprotein cholesterol
LMT:	lipid modifying therapy
LT:	lowest level term
Max:	maximum
MDRD:	modification of the diet in renal disease
MedDRA:	Medical Dictionary for Regulatory Activities
MI:	myocardial infarction
Min:	minimum
mITT:	modified intent-to-treat
PAD:	peripheral arterial disease
PCSA:	potentially clinically significant abnormality
PT:	preferred term
Q1:	first quartile
Q2W:	every 2 weeks

Q3:	third quartile
RBC:	white blood cells, red blood cells
SAE:	serious adverse event
SBP:	systolic blood pressure
SC:	subcutaneous
SD:	standard deviation
SE:	standard error
SIAQ©:	self-injection assessment questionnaire
SMQ:	standardized MedDRA query
SOC:	system organ class
TEAE:	treatment-emergent adverse event
TG:	triglyceride
Total-C:	total cholesterol
ULN:	upper limit of normal range

## 1 OVERVIEW AND INVESTIGATIONAL PLAN

### 1.1 STUDY DESIGN

This trial is to be conducted as a multi-country, multi-center prospective, single arm, open-label, phase IIIb clinical trial.

After enrollment, patients received study treatment (alirocumab) 150 mg subcutaneous (SC) once every 2 weeks (Q2W) or 75 mg SC Q2W. The dose could be adjusted according to the investigator, based on treatment response.

Alirocumab was administered on top of stable maximally tolerated statin therapy ± other lipid modifying therapy (LMT) over a period of at least 12 weeks and until the product becomes commercially available and reimbursed but for a period not exceeding 30 months of treatment.

In each country, patient recruitment was scheduled to end when alirocumab became commercially available and reimbursed. In this case, study treatment could be switched to the commercial product (or another LMT) once the patient had completed the minimum of 12 weeks of study treatment. As a consequence, the total duration of study depend on countries with a minimum of 12 weeks in each participating country and the number of patients at each time point beyond 12 weeks of study treatment is likely to be very variable.

During the course of the study, the investigator managed, based on his/her own clinical judgment and low density lipoprotein cholesterol (LDL-C) value, adjustment of alirocumab doses (either up-titration from 75 to 150 mg Q2W or down-titration from 150 to 75 mg Q2W, or maintenance of the dose). In case a modification of the current dose was decided, the patient was contacted by the site staff and an unscheduled visit was planned to dispense the new treatment kit and retrieve the current one.

The study consists of:

- A screening period of up to 3 weeks, including a training injection during which the patient or another designated person (such as spouse, relative, etc) was trained to self-inject/inject. An optional dedicated visit could be scheduled as needed.
- An open-label treatment period with alirocumab of at least 12 weeks and until the product becomes commercially available and reimbursed. However, the open label treatment period cannot exceed 30 months.
- An end-of-treatment (EOT)/end-of-study (EOS) visit taking place at least 2 weeks after the last study treatment injection.

Note that the original version of protocol included a post-treatment follow-up visit taking place 10 weeks after the last injection for patients who prematurely discontinued alirocumab for any reason as well as for those who switched to another LMT. For those patients who participated in the study under the original version of protocol, the EOT visit and the EOS visit did not occur at the same time (see [Section 1.5](#)).

The end of the study per patient is the last protocol planned visit or the resolution/stabilization of all serious adverse events (SAEs) and adverse events of special interest (AESIs), or death, whichever comes last.

During the screening and inclusion visits, it was checked that patients were not adequately controlled with a maximally tolerated dose of statin\* with or without other LMT, all at stable doses for at least 4 weeks prior to the screening visit and could be classified in at least one of the following groups to be included in the study:

- A. Patients suffering from heterozygous familial hypercholesterolemia (heFH) with LDL-C concentrations  $\geq 160$  mg/dL (4.2 mmol/L) despite treatment.
- B. Patients suffering from heFH with LDL-C concentrations  $\geq 130$  mg/dL (3.4 mmol/L) despite treatment and two or more cardiovascular (CV) risk factors among this list:
  - Baseline LDL-C  $> 6.46$  mmol/L (250 mg/dL) at the time of the familial hypercholesterolemia (FH) diagnosis (before treatment).
- Family history of premature-onset coronary heart disease (CHD)
  - CHD (first-degree male relative with onset before age 55 years; first-degree female relative with onset before age 65 years),
  - Metabolic syndrome (cf. definition in protocol),
  - High density lipoprotein cholesterol (HDL-C)  $< 1.03$  mmol/L (0.40 g/L),
  - Hypertension (blood pressure [BP]  $> 140/90$  mmHg or drug treatment),
  - Lp(a)  $\geq 0.50$  g/L (1.78  $\mu$ mol/L),
  - Tendon xanthoma.
- C. Patients suffering from heFH with LDL-C concentrations  $\geq 130$  mg/dL (3.4 mmol/L) despite treatment and one of the following characteristics:
  - **established CHD or other cardiovascular disease (CVD)** (history of acute myocardial infarction [MI], ischemic stroke, peripheral arterial disease [PAD], coronary or peripheral arterial revascularization, stable or unstable angina, transient ischemic attack, carotid artery stenosis  $\geq 50\%$ , aortic abdominal aneurysm),
  - **drug treated type 2 diabetes mellitus or type 1 with target organ damage**

## 1.2 OBJECTIVES

### 1.2.1 Primary objective

The primary objective of this study for patients with severe hypercholesterolemia at risk for subsequent CV events and not adequately controlled with currently available LMT is to provide access to alirocumab ahead of commercial availability and to document the overall safety and tolerability of alirocumab in this patient population.

### 1.2.2 Secondary objectives

The secondary objectives are:

- To document the effect of alirocumab on LDL-C levels as well as non-HDL-C, total cholesterol (Total-C), HDL-C, triglyceride (TG) levels after 12 weeks of treatment.
- To document patient acceptability of self-injection (Self Injection Assessment Questionnaire [SIAQ©]) throughout the study.

## 1.3 DETERMINATION OF SAMPLE SIZE

No formal sample size calculation has been done. The Safety analyses of this study will be descriptive. The table below provides the precision (95% Confidence Interval [CI]) associated to a variety of AE rates for an anticipated sample size of around 1300 patients:

[figure not shown]
**Table 1 - Expected 95% CI for various event rates**

Adverse event rates	10%	20%	30%	40%	50%
95% CI	[8.4%; 11.6%]	[17.8%; 22.2%]	[27.5%; 32.5%]	[37.3%; 42.7%]	[47.3%; 52.7%]

For a rare non observed event, by using the rule of three, it can be estimated that the upper limit of the 95% CI of the event rate is approximately equal to 3 divided by the expected number of patients, ie, 0.23%.

## 1.4 STUDY PLAN

The study duration includes up to 3 weeks of screening period, a minimum of 12 weeks and up to a maximum 30 months of open label study treatment period and an end-study visit at least 2 weeks after the last study treatment injection. Note that the graphical study design displayed below corresponds to the amended protocol (see [Section 1.5](#) for further details about the modifications with respect to the initial version of the protocol).

## 1.5 MODIFICATIONS TO THE STATISTICAL SECTION OF THE PROTOCOL

This section summarizes major changes to the protocol statistical section with emphasis on changes after study start (after the first patient was enrolled).

The protocol history table below gives the timing, rationale, and key details of major changes to the protocol statistical section.

The first patient was enrolled on 08 July 2015.

There was one global protocol amendment to the study protocol, introduced after the first patient was enrolled. The major change was about the final on-site visit.

In the newly amended version of the protocol, only one final on-site visit called “EOT/EOS” is required, for all enrolled patients. It has to be performed at least 14 days after the last study treatment injection. However, Investigators should continue to follow-up related SAE or AESI that are ongoing at this final visit until their resolution or stabilization.

In the original version of the protocol, a follow up on-site visit was required to take place:

- Either 2 weeks after last treatment injection for patients who would switch to commercial alirocumab.
- Or 10 weeks after last treatment injection for patients who would prematurely discontinue the treatment irrespective of the reason and for those who would switch to another compound.

**Table 2 - Protocol amendment statistical changes**

Amendment Number	Date Approved	Rationale	Description of statistical changes
Clinical Trial Amendment no. 5 (ie, the first global protocol amendment)	01Mar2016	
Reassessment of the number of patients planned to be enrolled from 1100 initially planned to 1300
 
Streamlining of the requirements for the end of study
 
Standardization across the protocols for observational studies
 
Clarification regarding the LDL-C assessment given that efficacy is a secondary endpoint and that no central lab is utilized in this study
 
Although there is no formal interim analysis, some statistical analyses might be performed before the end of the study in order to support a dossier of reimbursement if required by health authorities in some countries
	
Modifications of the table of expected 95% CI for various adverse events rates
 
Only one final on-site visit called “EOT/EOS Visit” is required
 
Modification of the list of the AE of special interest
 
The Friedewald formula to assess LDL-C will be used even in case TG is elevated (>400 mg/dL)
 
Some statistical analyses might be performed before the end of the study

In addition to the medical history of specific interest to be described such as quoted in the protocol (CHD, CHD risk equivalents...), the multiple manifestations of CV disease (see [Section 2.1.1](#)) was added due to the very high risk of CV event profile of patients enrolled in this study.

Some secondary efficacy analyses were added compared to the original version of the protocol, mainly regarding the occurrence of very low LDL-C level and the associated changes in treatment (see [Section 2.4.4.4](#)) in order to better characterize these cases.

Additional descriptive analyses were added to document the adherence to statins according to alirocumab dose and the achieved LDL-C.

Two subgroups that are of particular clinical interest due to the very high risk of CV event profile of these patients were added, namely primary CVD prevention and the subgroup of patients with multiple manifestations of CV diseases.

The definition of the modified intent-to-treat (mITT) population was slightly changed in order to take into account the fact that no imputation will be performed for the missing LDL-C values. Consequently, the availability of a calculated LDL-C value within the analysis window associated to Week 12 is required (See [Section 2.3.1](#)).

In the SIAQ© population is included the condition of the patient who followed the training injection.

## **1.6 STATISTICAL MODIFICATIONS MADE IN THE STATISTICAL ANALYSIS PLAN**

Not applicable.

## 2 STATISTICAL AND ANALYTICAL PROCEDURES

### 2.1 ANALYSIS ENDPOINTS

#### 2.1.1 Demographic and baseline characteristics

The baseline value is defined as the last value obtained before the date of the first injection of alirocumab.

All baseline safety and efficacy parameters (apart from those listed below) are presented along with the summary statistics in the safety and efficacy sections ([Section 2.4.4](#) and [Section 2.4.5](#)).

##### *Demographic characteristics*

Demographic variables are:

- Gender (Male, Female)
- Race (White/Caucasian, Black, Asian/Oriental, Multiracial, other)
- Ethnicity (Hispanic, Not Hispanic)
- Age in years (quantitative and qualitative variable: <45,  $\geq 45$  to <65,  $\geq 65$  to <75, and  $\geq 75$  years)

##### *Medical history*

Medical history of specific interest includes:

- Coronary heart disease.
- Coronary heart disease risk equivalents.
- Cerebrovascular disease.
- Cardiovascular risk factors other than hypercholesterolemia (hypertension, type 2 diabetes, type 1 diabetes, family history of premature CHD). Smoking status will be summarized separately.
- Family history of type 2 diabetes.
- Patient's allergies (described using all pre-printed terms collected in the medical allergic history eCRF page).
- Familial allergic history.
- Multiple manifestations of CV disease.
- Primary and secondary CVD prevention.

The CHD, CHD risk equivalents and multiple manifestations of CV disease will be based on items or combination of items pre-printed in the dedicated CV medical history eCRF page and will also be searched in the list of other CV medical history.

*CHD (regardless if it is ongoing or not) corresponds to one of the following items:*

- Acute myocardial infarction
- Silent myocardial infarction
- Unstable angina
- Coronary revascularization procedures
- Other clinically significant CHD (diagnosed by invasive or non-invasive testing)

*CHD risk equivalents (regardless if it is ongoing or not) corresponds to one of the following items:*

- Peripheral arterial disease (as defined in [Section 2.5.1](#))
- Ischemic stroke
- Chronic kidney disease
- Known history of diabetes mellitus (type 1 or 2) AND 2 or more additional risk factors among:
  - History of hypertension
  - History of microalbuminuria or macroalbuminuria or proteinuria (>2+ at screening)
  - History of diabetic retinopathy
  - Known family history of premature CHD (before 55 years of age in male, 65 years of age in female first degree relatives)

*Multiple manifestations of CV disease (regardless if it is ongoing or not) are defined as follows:*

- Two arterial beds:
  - CHD and cerebrovascular disease
  - CHD and PAD
  - Cerebrovascular disease + PAD
- Three arterial beds: CHD and cerebrovascular disease and PAD (as defined in [Section 2.5.1](#))

*Cerebrovascular disease corresponds to one of the following items:* carotid surgery or stenting, hemorrhagic stroke, ischemic stroke.

In addition, patients' status as primary and secondary CVD prevention will be summarized.

*Secondary CVD prevention is defined as patients with at least one of the following conditions:*

- History of acute myocardial infarction
- Ischemic stroke
- Peripheral arterial disease
- Coronary or peripheral arterial revascularization
- Stable or unstable angina
- Transient ischemic attack
- Carotid artery stenosis  $\geq 50\%$
- Aortic abdominal aneurysm

All other patients will be classified as primary CVD prevention.

All medical/surgical history information in the eCRF (preprinted terms or terms mentioned in free text) will be coded using the version of Medical Dictionary for Regulatory Activities (MedDRA) currently in effect at Sanofi at the time of database lock.

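### SAP 2.1.1 labels as primary CVD prevention some patients whom the same section counts as having CHD or cerebrovascular disease

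*SAP*

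**What the plan says.** SAP 2.1.1 (Medical history) holds several definitions that bear on each other.

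- **CHD** has five items. Two of them are "Silent myocardial infarction" and "Other clinically significant CHD (diagnosed by invasive or non-invasive testing".
- **Cerebrovascular disease** has three: "carotid surgery or stenting, hemorrhagic stroke, ischemic stroke".
- **Multiple manifestations of CV disease** means disease in at least two of three beds: CHD, cerebrovascular disease and PAD. PAD itself is defined in SAP 2.5.1.
- **Secondary prevention** has a list of its own: "Secondary CVD prevention is defined as patients with at least one of the following conditions". The list covers acute MI, ischemic stroke, PAD, coronary and peripheral revascularization, angina of either kind, TIA, carotid stenosis of at least 50%, and abdominal aortic aneurysm.
- **Primary prevention** is everyone else: "All other patients will be classified as primary CVD prevention".

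SAP 1.5 gives the labels a use. Two subgroups were added because of their clinical interest, "namely primary CVD prevention and the subgroup of patients with multiple manifestations of CV diseases". SAP 2.1.1 also has primary and secondary status summarized as a baseline characteristic.

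**The concern.** A reader of the report will take primary prevention to mean no established cardiovascular disease. Under the SAP it means only that nothing on one particular list was recorded. Because membership is by default, any disease item missing from that list falls into the primary-prevention group. If the list is narrower than the section's own definitions of CHD and cerebrovascular disease, the subgroup is mislabelled for some patients. The two subgroups singled out in SAP 1.5, which sound like opposite ends of the risk range, could then share members.

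**Working it through.** No figure in the plan attaches to this point, so the check compares the lists item by item.

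**Step 1. Is each disease item in SAP 2.1.1 on the secondary-prevention list?**

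| Item | Counted in SAP 2.1.1 as | On the secondary list? |
|---|---|---|
| Acute MI | CHD | Yes |
| Silent MI | CHD | No |
| Unstable angina | CHD | Yes |
| Coronary revascularization | CHD | Yes |
| Other clinically significant CHD | CHD | No |
| Ischemic stroke | Cerebrovascular | Yes |
| Carotid surgery or stenting | Cerebrovascular | No |
| Hemorrhagic stroke | Cerebrovascular | No |
| PAD | PAD | Yes |

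Two of five CHD items and two of three cerebrovascular items do not trigger secondary prevention. PAD leaves no gap. Hemorrhagic stroke hardly matters, because exclusion criterion E 08 bars patients with a known history; only deviators could be affected.

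**Step 2. Does a broad reading of the list close the gap?**

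- The MI entry is "History of acute myocardial infarction". The CHD definition lists silent and acute MI as separate items, so one cannot be assumed to include the other.
- The carotid entry is "Carotid artery stenosis" of at least 50%. It names a stenosis, not a procedure.
- Carotid stenting is not clearly a peripheral revascularization either. The PAD definition in SAP 2.5.1 has no carotid item, and protocol criterion E 07 names carotid procedures separately from those for peripheral vascular disease.

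**Step 3. Can one patient be in both subgroups?** That needs two beds, each reached only through omitted items. PAD is on the list, so any pairing with PAD makes the patient secondary. This leaves 2 CHD items × 2 cerebrovascular items = 4 pairs. Setting hemorrhagic stroke aside leaves 2 × 1 = 2 pairs: silent MI, or other clinically significant CHD, together with carotid surgery or stenting. Either pair, with no listed condition recorded, puts the patient in both groups.

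**Step 4. Who can be affected?**

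- Group D and the CVD route into group C require conditions from the same set as the secondary list, so those patients are secondary.
- Group E requires a qualifying event: acute MI, ischemic stroke, ischemia-driven revascularization, unstable angina or TIA. All map to the list, unless the revascularization was carotid and nothing else was recorded.
- Group A needs only heFH and LDL-C of at least 160 mg/dL. Group B needs heFH and risk factors. Group C can be met by diabetes or by family history. None of these routes requires a listed condition, so the exposed patients are here.

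**Step 5. How many?** The count would be 1300 × p × q, where p is the share labelled primary prevention and q is the share of those whose only disease is an omitted item. The documents give neither. As pure assumption, p from 10% to 40% and q from 2% to 20% give:

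- low end: 1300 × 0.10 × 0.02 = 2.6, about 3 patients
- high end: 1300 × 0.40 × 0.20 = 104 patients

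The width of that range reflects the assumptions and tells us nothing about the trial.

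**The case against.** The strongest defense is that the secondary-prevention list has a clear source. It repeats the conditions that inclusion criteria C and D use for established CHD or other CVD, and SAP 2.4 uses that category as a subgroup. Tying secondary prevention to the eligibility definition is a reasonable choice, and the CHD and cerebrovascular lists serve a different purpose, counting history and arterial beds. This explains where the list came from. It does not justify the default: a list of conditions sufficient for entry was not written to show that everyone else is free of disease.

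Several limits do stand.

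- Many patients with an omitted item will also have a listed one. Someone with a carotid stent is classified correctly if stenosis of at least 50% is recorded.
- The CHD definition has no stable-angina item, so some entries under other clinically significant CHD may be stable angina, which is on the secondary list. How the eCRF records this cannot be seen. The firmest gap is silent MI and test-diagnosed CHD without angina or revascularization.
- SAP 2.4 names neither of the two added subgroups. Its list is introduced as examples, so their outputs are unclear rather than ruled out.
- The SAP never says that the two subgroups must exclude each other. That is an inference from their names, though a fair one.

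**Conclusion.** The inconsistency is real and follows from the text alone. Applied as written, SAP 2.1.1 labels as primary prevention a patient whose only recorded disease is silent MI, other clinically significant CHD, or carotid surgery or stenting, although the same section counts each as disease. Overlap with multiple manifestations is possible but rarer, since it needs an omitted item in each of two beds.

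The consequence is small. It touches one baseline summary and one descriptive subgroup. SAP 2.4 plans no formal tests, and the overall safety analysis, the overall mITT efficacy results and the inclusion-group, heFH and diabetes subgroups do not depend on the label.

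A reader might infer that the primary-prevention subgroup is heavily contaminated, or that the trial's safety conclusions are at risk. The documents support neither. They give no prevalence for the omitted items, exposure is essentially limited to the heFH routes that require no CVD, and no overall result uses this classification.

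The conclusion assumes that the list is applied literally, without an unstated coding rule that maps the omitted items onto listed ones.

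**What to change.** Before database lock, redefine secondary prevention in SAP 2.1.1 as any condition on the current list or any item that the section counts as CHD, cerebrovascular disease or PAD, with primary prevention as the remainder. This adds silent MI, other clinically significant CHD and carotid surgery or stenting and, for protocol deviators only, hemorrhagic stroke. Every patient with multiple manifestations is then secondary by construction. If the omissions are deliberate, the SAP should say so and give the reason.

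The cost is one sentence and a change to one derived variable. No new data are needed: SAP 2.1.1 already derives CHD and multiple manifestations from the CV history eCRF page and other recorded CV history. Protocol section 11 allows the plan to be revised, with the final plan issued before lock.

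There is one trade-off to note in the SAP. The secondary-prevention label will be slightly wider than the established CHD or other CVD wording of inclusion criteria C and D. That wording stays unchanged for eligibility.
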